3.4.5.3 Review and Oversight Requirements

3.4.5.4 Adverse Event Monitoring

Adverse Events (AEs) will be recorded on the Oncore database, all grade 3-5 expected and unexpected AEs will be recorded and updated at each visit.

Serious Adverse Event Reporting

Serious Adverse Event reporting will be in accordance with the UCSF- Committee on Human Research Regulations and Code of Federal Regulation Title 21 Volume 5 Part 312.32.

UCSF CHR website for guidance in reporting serious adverse events

http://www.research.ucsf.edu/chr/Guide/Adverse_Events_Guidelines.pdf

FDA website for guidance in reporting serious adverse events

<http://www.accessdata.fda.gov/scripts/cdrh/cfdocs/cfcfr/CFRSearch.cfm?fr=312.32>

MedWatch forms and information:

<http://www.fda.gov/medwatch/getforms.htm>

Serious Adverse events will be reported on the MedWatch form. A copy of the MedWatch report and CHR forms must be sent to CCC- DSMC at Box 1297. The date the SAE was sent to all required reporting agencies will be documented in Oncore, and hard copies of the report will be maintained in the regulatory files.

If the SAE is death and determined to be possibly, probably or definitely related to the investigational drug or any research related procedure the event must be reported to the DSMC Chair, or his designee with in 24 business hours. The reporting procedure is by personal communication via phone or in person with written documentation of the 1:1 communication via e-mail with a copy of the e-mail to DSMC Administrator and DSMC Coordinator.

If any of the above action occurs in multiple-institutional clinical trial coordinated by the UCSF-CCC, the Study Coordinator will insure that all participating sites are notified.

3.4.6 Review of Adverse Event Rates

If the study has an increase of unexpected or expected Adverse Events grade 3 or 4 above the rate reported in the Investigational Brochure or package insert, the increase rate of AEs will be reported to the DSMC at the time of Identification. The Chair and PI will discuss the finding and proceed with a written course of action. Each quarterly report will indicate if the AE incidence is within the scope of the investigational brochure or package insert. If at any time the Investigator stops enrollment or stops the study due to safety issues the DSMC Chair and Administrator must be notified within 24 business hours via e-mail. The DSMC must receive a formal letter within 10 business days and the CHR must be notified.

If any of the above action occurs in multiple-institutional clinical trial coordinated by the UCSF-CCC, the Study Coordinator will insure that all participating sites are notified.

3.4.7.1 Pregnancies

Any pregnancy that occurs during study participation should be reported. To ensure patient safety each pregnancy must also be reported to Novartis within 24 hours of learning of its occurrence. The pregnancy should be followed up to determine outcome, including spontaneous or voluntary termination, details of birth, and the presence or absence of any birth defects, congenital abnormalities or maternal and newborn complications.

3.4.7.2 Laboratory evaluations

- *please see section 3.4.1 for schedule for initial assessment and during follow up*

Hematology

Hematology must include hemoglobin, hematocrit, platelets, total white blood cell count (WBC) and differential. PT (INR) evaluation will be included for baseline evaluations.

Blood chemistry

Blood chemistry must include sodium, potassium, chloride, bicarbonate, calcium, glucose, creatinine, blood urea nitrogen, albumin, total protein, SGOT (AST), SGPT (ALT), total bilirubin, alkaline phosphatase, uric acid, phosphorus, serum lipid profile (triglycerides, total cholesterol, HDL and LDL).

Because accurate serum glucose and lipid measurements are required, patients should be fasting at the time of the blood sampling.

Hepatitis B Virus testing

Patients will be tested for the following hepatitis B serologic markers prior to enrolling on the trial: HBsAg, HBs Ab, and HBc Ab Total, and HBc IgM Ab.

HbsAg monitoring should be performed every 4 weeks if a patient tests positive for the hepatitis B antibodies without prior vaccination

Hepatitis C Virus testing

Patients will be tested for HCV Ab prior to enrolling on the trial.

3.4.7.3 Vital signs

Vital sign assessment consists of height (first visit), pulse, blood pressure, respiration rate, temperature and weight. Blood pressure, pulse and respiration rate should be measured on patients

3.4.7.4 Physical examination

Physical examination will be performed which must comprise a total body examination (general appearance, skin, neck, including thyroid, eyes, ears, nose, throat, lungs, heart, abdomen, back, lymph nodes, extremities and basic nervous system).

Please see 3.4.1 for detailed neurological assessment.

Significant findings made after the start of study drug which meet the definition of an Adverse Event must be recorded.

3.4.7.5 ECG

A standard 12 lead ECG is to be performed during screening and significant findings must be recorded.

3.4.7.6 Performance status

Performance status will be assessed.

- *Karnofsky score as outlined in 3.4.1.*

3.4.7.7 Special tests

- *MRI as outlined in 3.4.1; neurological evaluation as outlined in 3.4.1*

3.4.8 Drug levels and pharmacokinetic assessments

- *Drug levels will not be monitored*

4 Protocol amendments, or changes in study conduct

Any change or addition (excluding administrative) to this protocol requires a written protocol amendment that must be reviewed by Novartis and the investigator before implementation. Amendments significantly affecting the safety of subjects, the scope of the investigation or the scientific quality of the study require additional approval by the IRB at each study center. A copy of the written approval of the IRB must be provided to Novartis. Examples of amendments requiring such approval are:

1. increases in drug dose or duration of exposure of subjects,
2. significant changes in the study design (e.g. addition or deletion of a control group),
3. increases in the number of invasive procedures,
4. addition or deletions of a test procedure required for monitoring of safety.

These requirements for approval should in no way prevent any immediate action from being taken by the investigator or by Novartis in the interests of preserving the safety of all patients included in the trial. If an immediate change to the protocol is felt to be necessary by the

investigator and is implemented for safety reasons Novartis must be notified and the IRB at the center must be informed immediately. Amendments affecting only administrative aspects of the study do not require formal protocol amendments or IRB approval but the IRB must be kept informed of such administrative changes. Examples of administrative changes not requiring formal protocol amendments and IRB approval include:

1. changes in the staff used to monitor trials
2. minor changes in the packaging or labeling of study drug.

5 Data management

5.1 Data collection

- Investigators must record the information required by the protocol.

6 Statistical methods

6.1 Statistical methods

6.1.1. Stopping Rules

If the discontinuation rate due to toxicity is 20% or greater and the lower bound for the one-tailed 95% confidence interval is $> 10\%$, this strategy would not be considered feasible. At the time we observe any toxicity that requires permanent discontinuation of drug, we will estimate, with confidence intervals, the rate of toxicity. If there is a greater than 20% rate for discontinuation of drug during therapy the study will stop and we will assess the study design. Because the confidence interval may be calculated multiple times, the actual confidence level will be overstated. This increases the likelihood of rejecting the therapy due to toxicity. However, this is felt to be an acceptable risk in order to prevent continuation of a therapy that may have a toxicity rate that precludes its routine use.

If there is any treatment related mortality event, the study accrual will be suspended until all data pertaining to the event is reviewed by the Study Chair and co-investigators.

6.1.2. Endpoint Definitions and Sample Size

The following definitions will be used for statistical analysis:

- Response: Response is based on the best response. The best response is defined as the best objective status as measured by the sum of products of perpendicular diameters of all measurable lesions.
- Progression-free survival: Number of days from the day the patient was enrolled to the day the patient experiences an event of disease progression or recurrence or to the date of death if disease progression or recurrence is not reached. All events of disease progression or recurrence will be included, regardless of whether the event

occurred while the patient was still taking drug or had previously discontinued study drug. All events of death will be included for patients who had not experienced disease progression or recurrence. If the patient does not have an event of disease progression or recurrence nor as the patient died, the patient's data will be censored at the date of last contact with the patient.

- Overall survival: Number of days from the day the patient was enrolled until the date of death. If the patient is lost to follow-up, the patient's data will be censored at the date of last contact with the patient.

For this single-arm phase II trial, the primary endpoint will be 6-month progression-free survival (PFS-6). Patients will be analyzed based on intention to treat. The primary determination of treatment success will be based on the results for those patients who are shown to still be low-grade. The intent is to perform the primary analysis at the time the 6 month PFS is known for all patients.

Precise documentation of prognosis among recurrent low grade glioma patients treated with targeted therapy is limited in literature. A recent study based on the experience of the North American Brain Tumor Consortium (NABTC) was conducted to assess whether progression status at 6 months predicts survival from that time among recurrent high-grade glioma adult patients (Lamborn, Yung et al. 2008). In that study, it was reported that the estimated PFS-6 among recurrent grade III glioma patients who were not treated with temozolomide, a chemotherapy which is part of the standard of care for newly diagnosed gliomas, is approximately 17%. Since we expect patients with recurrent low grade gliomas to have better prognosis than grade III patients, we consider the lower threshold for the probability of 6-month PFS to be 17%. The calculation of sample size is based on a binary endpoint with the goal to increase 6-month PFS rate to 40%. This translates into a hazard ratio of 0.52 (experimental/historical). 40 patients will provide over 90% power using a one-sided test with alpha of 0.05.

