In an effort to reduce the use of radiotherapy, several studies have evaluated the use of chemotherapy as initial treatment of LGG. Tumor regressions using a combination of procarbazine, lomustine and vincristine in patients with an oligodendroglial component has been demonstrated (Buckner et al. 2003; Stege et al. 2005). More recently, temozolomide showed activity as treatment for recurrent LGG. However, the role of chemotherapy as up-front treatment of LGG continues to be evaluated (Grier and Batchelor, 2003; Hoang-Xaun et al. 2004; Brada et al. 2003).

The role of chemotherapy in adult patients with recurrent LGG has also not been extensively investigated (Quinn et al. 2003; Pace et al. 2003; Soffietti et al. 1998). Nitrosourea based chemotherapy and temozolomide have both been evaluated. In small studies, temozolomide

appears to have response rates ranging from 47-61% and 1 year progression free survival from 39-76% (Quinn et al. 2003; Pace et al. 2003). Although these numbers appear promising for the treatment of recurrent LGG with chemotherapy, other treatment strategies are needed for this patient population, especially in the setting of progression to malignant glioma. With a better understanding of the signaling pathways important for tumor growth and invasion, novel targeted therapies are being evaluated.

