3.1 Overall study design

A single-arm, one-stage phase II trial of RAD001 will be undertaken. Sixty patients will be enrolled. The target population will be patients with a diagnosis of low-grade glioma who experience a recurrence and who undergo a biopsy or subtotal resection at the time of recurrence with pathologic evidence of recurrent glioma. The purpose of this study is to accrue patients to evaluate a pharmacologic agent.

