3.3.3 Concomitant therapy

All concomitant medications administered within 14 days of enrollment through treatment termination should be reported to the investigator and recorded in the Case Report Form (CRF). In particular, corticosteroid dosing will be recorded as use of corticosteroids may affect the appearance of T2 changes on MRI imaging. In addition, the definition of response is based on corticosteroid use (see section 3.42).

Patients will be instructed not to take any additional medications (including over-the-counter products) during the course of the study without prior consultation with the investigator. At each visit, the investigator will ask the patient about any new medications he/she is or has taken after the start of the study drug.

All Concomitant medications/Significant non-drug therapies taken \leq 30 days prior to start and after start of study drug, including physical therapy and blood transfusions, should be recorded.

The following restrictions apply during the entire duration of the study:

- No other investigational therapy should be given to patients.
- No anticancer agents other than the study medication should be given to patients. If such agents are required for a patient then the patient must first be withdrawn from the study.
- Oral contraceptives in preclinical and clinical data have shown everolimus to have CYP3A4 inhibitory activity rather than induction activity, induction of metabolism of contraceptive hormones by everolimus is unlikely. Consequently, administration of everolimus should not reduce the efficacy of oral contraceptives.

Inhibitors of CYP3A4 and/or PgP

- Co-administration with strong inhibitors of CYP3A4 (e.g., ketoconazole, itraconazole, ritonavir) or P-glycoprotein (PgP) should be avoided

- Seville orange, star fruit, grapefruit and their juices affect P450 and PgP activity. These juices are potent CYP3A4-inhibitors. Concomitant use should be avoided
- Co-administration with moderate CYP3A4 inhibitors (e.g., erythromycin, fluconazole) or PgP inhibitors should be used with caution. If patient requires co-administration of moderate CYP3A4 inhibitors or PgP inhibitors, reduce the dose of RAD001 to 2.5 mg daily. Additional dose reductions to every other day may be required to manage toxicities. If the inhibitor is discontinued the RAD001 dose should be returned to the dose used prior to initiation of the moderate CYP3A4/PgP inhibitor after a washout period of 2 to 3 days.

Inducers of CYP3A4 and/or PgP

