3.4.1.3 Follow-Up Assessments

- Protocol Completion Assessment:
 - After administration of RAD001 for two years, patients will be offered the opportunity to continue treatment. There is no limit to the course of treatment an individual patient may receive. However, the patient will continue to be evaluated at 3 month intervals while on RAD001 and a decision to discontinue treatment after 2 years of therapy will be made on clinical grounds.
 - All patients must be observed for safety for 30 days following the last dose of RAD001 prior to withdrawal from study. This defines study completion.
 - Physical examination and comprehensive neurologic examination and grading, vital signs including weight, Karnofsky Performance status, all laboratory values, and MRI of the brain must be repeated within 2 weeks of the last day of study only if these have not been evaluated within 14 days, inclusive, prior to the date of withdrawal from study.
- Long-term Follow-up:
 - Patients will be followed according to routine clinical practice after removal from protocol therapy or until death, whichever occurs first.
 - Patients removed from protocol therapy for unacceptable adverse events will be followed until resolution or stabilization of the adverse event.
 - All patients will be followed for PFS and OS while on protocol therapy and while still receiving subsequent routine clinical care. Patients off protocol therapy will continue to be followed for PFS and OS only.

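### PFS-6 has no rule for another anti-tumour therapy started before month 6 without progression, so a single-arm success could partly reflect that therapy; a supportive analysis and one data item would show whether it does

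*Combined protocol and SAP*

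**What the plan says.** Section 3.1: "A single-arm, one-stage phase II trial of RAD001 will be undertaken". Section 6.1.2 measures progression-free survival from enrolment to progression, recurrence or death. It counts events on and off RAD001 alike: "All events of disease progression or recurrence will be included, regardless of whether the event" came during treatment or after it had stopped. Without an event, "the patient's data will be censored at the date of last contact with the patient". The population rule is "Patients will be analyzed based on intention to treat".

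Other anticancer agents are not allowed alongside RAD001. Section 3.3.3 adds: "If such agents are required for a patient then the patient must first be withdrawn from the study". Section 3.4.1.3 keeps PFS and OS follow-up running during later routine care: "Patients off protocol therapy will continue to be followed for PFS and OS only".

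Section 6.1.2 sets the lower threshold for PFS-6 at 17%, an estimate from recurrent grade III patients who had not been treated with temozolomide, and the target at 40%. Section 1.1.3.4 describes small temozolomide studies in recurrent low-grade glioma with "1 year progression free survival from 39-76" per cent.

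Neither Section 6.1.2 nor Section 6.1.4 makes the start of a new anti-tumour therapy an event, a censoring point or the subject of a sensitivity analysis.

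**The concern.** Take a low-grade patient who stops RAD001 at month 2 without progression, because of toxicity, withdrawal of consent or a dosing delay of more than 28 days. The patient starts temozolomide and is stable at month 6. Under the rules as written this patient is progression-free at 6 months and supports the claim that RAD001 lifts PFS-6 above 17%.

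In a randomised trial a control arm would show what later therapy contributes. Here the comparator is a fixed number, and the text ties that number to patients without temozolomide. If the later therapy works, the error favours RAD001. It would arise even if every off-drug patient were scanned on schedule, so better follow-up alone does not remove it.

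Patients who switch because they have progressed are not affected, since their event is already counted.

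**Working it through.** **1. The plan's own figure.** Section 6.1.2 gives N = 40 low-grade patients, 17% against 40%, one-sided alpha 0.05 and power over 90%. The smallest r with P(X ≥ r | 40, 0.17) ≤ 0.05 is r = 12.
- Error: P(X ≥ 12 | 40, 0.17) = 3.0% (r = 11 would give 6.6%).
- Power: P(X ≥ 12 | 40, 0.40) = 92.9%.
- Hazard ratio: ln 0.40 / ln 0.17 = 0.517, which agrees with the stated 0.52.

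The sample-size statement reproduces. The 12-of-40 cut is derived here from the binary design basis. The plan does not print it, and its primary analysis is a Kaplan-Meier estimate with a 95% interval.

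**2. Inputs for the illustration.** All are assumptions except where a source is named.
- RAD001 itself gives exactly the 17% null, with constant hazard.
- k of the 40 switch at month t, and all k come from patients still progression-free at t.
- After the switch the hazard is that of a therapy with 1-year PFS y = 0.39 or 0.76 (range from Section 1.1.3.4).
- k = 2, 3 or 4. The documents give no switch rate. Section 3.2.5 reports 7% permanent discontinuation for adverse reactions in the renal cell trial, and 0.07 × 40 = 2.8, about 3. That is a discontinuation rate, not a switch rate.

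**3. Formulas.**
- Still progression-free at t: S(t) = 0.17^(t/6). S(2) = 0.554, or about 22 of 40. S(4) = 0.307, or about 12 of 40.
- Chance of reaching month 6 for those who stay on RAD001: c = 0.17 / S(t), which is 0.307 at t = 2 and 0.554 at t = 4.
- Chance for switchers: q = y^((6 − t)/12), which is 0.731 to 0.913 at t = 2 and 0.855 to 0.955 at t = 4.
- Expected PFS-6 = 0.17 + (k/40)(q − c). For k = 4, t = 2, y = 0.39: 0.17 + 0.1 × (0.731 − 0.307) = 0.212.
- False success = P(X ≥ 12), where M ~ Bin(40, S(t)) and X = Bin(M − k, c) + Bin(k, q), summed over M.

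**4. Results** (each range runs from y = 0.39 to y = 0.76).

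| Switchers | Month-2 switch: expected PFS-6 | False success | Month-4 switch: expected PFS-6 | False success |
|---|---|---|---|---|
| 0 | 17% | 3.0% | 17% | 3.0% |
| 2 | 19.1-20.0% | 5.8-7.2% | 18.5-19.0% | 4.6-5.1% |
| 3 | 20.2-21.5% | 7.8-10.7% | 19.3-20.0% | 5.6-6.7% |
| 4 | 21.2-23.1% | 10.4-15.6% | 20.0-21.0% | 6.8-8.6% |

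**5. Cost of counting switchers as failures.** Let true PFS-6 be 40% and let a share s switch independently of outcome. Power is P(X ≥ 12 | 40, 0.40(1 − s)).
- s = 5%: success probability 0.38, power 88.7%.
- s = 10%: success probability 0.36, power 83.0%.
- s = 0: power 92.9%.

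**The case against.** The strongest defence is that the rule is a recognised treatment-policy choice. Counting progression after drug is stopped adds failures and avoids informative censoring, and it fits intention to treat. That stands, and it is why the primary definition need not change.

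Switching may also be rare. Section 1.1.3.4 lists surveillance with treatment at progression as an option for residual low-grade glioma after surgery, so not everyone who stops RAD001 early would start something else before month 6. This stands too: the bias could be negligible.

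Four stronger readings are tempting, and the documents do not support them.
- *False success is likely.* A reader might leave everyone else at 17% and add switchers at a 6-month rate of √0.39 to √0.76 (62-87%). That gives 12-21% with four switchers and 33-64% with eight. But switchers must come from patients still progression-free, which lowers the rate among the rest. And eight of 40 is not a rate the plan tolerates. At 20% the exact one-sided 95% lower bound is 10.4%, so if the eight stopped for toxicity, both conditions in Section 6.1.1 for calling the strategy infeasible would be met.
- *A poorly tolerated drug is rewarded.* Section 6.1.1 judges tolerability separately and can stop the study.
- *The switch date is not collected.* Section 3.3.3 has one sentence that ends recording at treatment termination, and another that covers medication and non-drug therapy after the start of study drug with no end date. Collection is not assured, but its absence is not established.
- *The 17% excludes all later therapy.* The text says only that those patients were not treated with temozolomide. How the source handled other later therapy is not stated.

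**Conclusion.** The point holds as a gap in the endpoint definition. Followed as written, the plan credits RAD001 with progression-free time gained on another therapy started before month 6, and no control arm or planned analysis would reveal it. The sample-size arithmetic is sound.

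The size is unknown. Under the stated assumptions (true PFS-6 of 17%, the 12-of-40 cut, constant hazards, switches at months 2 to 4, temozolomide-like benefit), the 3.0% error becomes about 5-7% with two switchers, 6-11% with three and 7-16% with four. If switched patients gained less, the figures would be smaller.

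A reader might conclude that the primary analysis must be replaced. The documents do not support that. Which strategy is primary is a choice of estimand, and counting switchers as failures takes power below the stated 90% even at 5% switching. This is a low-cost improvement that would show whether a success claim depends on another treatment.

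**What to change.** Keep the intention-to-treat definition as primary and make three additions before analysis.

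1. **Section 3.4.1.3:** for every patient off protocol therapy, record the type and start date of the first subsequent anti-tumour therapy (drug, radiotherapy or tumour resection).
2. **Section 3.3.3:** reconcile the two sentences on how long medication is recorded, and reconcile the withdrawal wording with the continued PFS follow-up in Section 3.4.1.3.
3. **Sections 6.1.2 and 6.1.4:** add text such as the following. *In a supportive analysis of PFS-6 in low-grade patients, a patient who starts any other anti-tumour therapy before the 6-month landmark without documented progression is counted as not progression-free on RAD001. The number of such patients will be reported. If the success conclusion differs between the primary and supportive analyses, it will not be attributed to RAD001 alone.*

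The cost is one follow-up item and a short paragraph. The supportive analysis is conservative: it scores toxicity-driven switches as failures, and at a true PFS-6 of 40% its power is 88.7% with 5% switching and 83.0% with 10%. It should therefore be read beside the primary result and not replace it.
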